10.6 Medication error

For the purposes of this clinical study a medication error is an unintended failure or mistake in the treatment process for an AstraZeneca study drug that either causes harm to the patient or has the potential to cause harm to the patient.

A medication error is not lack of efficacy of the drug, but rather a human or process related failure while the drug is in control of the study site staff or patient.

Medication error includes situations where an error

- Occurred
- Was identified and intercepted before the patient received the drug
- Did not occur, but circumstances were recognized that could have led to an error

Examples of events to be reported in clinical studies as medication errors:

- Drug name confusion
- Dispensing error e.g. medication prepared incorrectly, even if it was not actually given to the patient
- Drug not administered as indicated, for example, wrong route or wrong site of administration

Clinical Study Protocol

Investigational Drug Substance: MEDI4736 Sirolimus (Rapamune)

Study Number **19-20015**

Edition Number: 4

Date: **11 February 2022**

- Drug not taken as indicated e.g. tablet dissolved in water when it should be taken as a solid tablet
- Drug not stored as instructed e.g. kept in the fridge when it should be at room temperature
- Wrong patient received the medication (excluding IVRS/IWRS errors)
- Wrong drug administered to patient (excluding IVRS/IWRS errors)

Examples of events that **do not** require reporting as medication errors in clinical studies:

- Errors related to or resulting from IVRS/IWRS - including those that lead to one of the above listed events that would otherwise have been a medication error
- Patient accidentally missed drug dose(s) e.g. forgot to take medication
- Accidental overdose (will be captured as an overdose)
- Patient failed to return unused medication or empty packaging
- Errors related to background and rescue medication, or standard of care medication in open label studies, even if an AZ product

Medication errors are not regarded as AEs but AEs may occur as a consequence of the medication error.

If a medication error occurs in the course of the study, then the Investigator or other site personnel informs Sponsor within 1 day i.e., immediately but **no later than 24 hours** of when he or she becomes aware of it.

The Sponsor works with the Investigator to ensure that all relevant information is completed within 1 or 5 calendar days. The Sponsor must report to AstraZeneca Patient Safety using the designated Safety e-mailbox (see Section 10.5 for contact information) within 7 calendar days or sooner when required (see Section 10.5) if there is an SAE associated with the medication error and within 30 days for all other medication errors.

11. STATISTICAL METHODS AND SAMPLE SIZE DETERMINATION

11.1 Description of analysis sets

11.1.1 Safety analysis set

All enrolled patients will be evaluable for safety analyses from the time of their first treatment with sirolimus and/or durvalumab.

11.1.2 Efficacy analysis set

The primary and secondary efficacy analyses will include all enrolled patients who have received at least one dose of durvalumab, underwent resection and who do not have EGFR mutant tumors (efficacy population).

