Other adverse events (toxicity) will be listed and summarized overall and by dose level. Adverse events will also be listed by severity, seriousness, and by system organ class. The number and percentage of subjects who experience AEs will be presented in tabular and/or graphical format and summarized descriptively, where appropriate. No formal statistical comparison between the dose levels or PD-L1 will be performed. AEs will be presented with and without regard to causality based on the investigator's judgment. The frequency of overall toxicity, categorized by toxicity grades 1 through 5, will be described. Additional summaries will be provided for AEs that are observed with higher frequency.

Efficacy Analyses:

The primary and secondary efficacy analyses will include all enrolled patients who have received at least one dose of durvalumab, underwent resection and who do not have EGFR mutant tumors (*efficacy population*).

Primary Efficacy Endpoint

The effectiveness of sirolimus followed by durvalumab will be assessed by complete pathologic response rate in the *efficacy population*. If the null hypothesis is rejected then this is evidence that the response rate exceeds 10% when sirolimus followed by durvalumab is given before resection. The one-sided 95% confidence interval (CI) for complete pathologic response will be reported. Exact binomial test will be used to compare the estimated complete pathologic response rate to the historical reference.

Secondary Efficacy Endpoints

The complete pathologic response rates for PDL-1 negative and PDL-1 positive patients in the *efficacy population* will be presented separately.

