1.6.2 Overall risks

Monoclonal antibodies directed against immune checkpoint proteins, such as programmed cell death ligand 1 (PD-L1) as well as those directed against programmed cell death-1 (PD-1) or cytotoxic T-lymphocyte antigen-4 (CTLA-4), aim to boost endogenous immune responses directed against tumor cells. By stimulating the immune system however, there is the potential for adverse effects on other tissues.

Most adverse drug reactions seen with the immune checkpoint inhibitor class of agents are thought to be due to the effects of inflammatory cells on specific tissues. These risks are generally events with a potential inflammatory or immune mediated mechanism and which may require more frequent monitoring and/or unique interventions such as immunosuppressants and/or endocrine therapy. These immune mediated effects can occur in nearly any organ system,

Clinical Study Protocol

Investigational Drug Substance: MEDI4736 Sirolimus (Rapamune)

Study Number **19-20015**

Edition Number: 4

Date: **11 February 2022**

and are most commonly seen as gastrointestinal AEs such as colitis and diarrhea, pneumonitis/interstitial lung disease (ILD), hepatic AEs such as hepatitis and liver enzyme elevations, skin events such as rash and dermatitis and endocrinopathies including hypo- and hyper-thyroidism.

Neo-adjuvant studies additionally pose the risk of delaying or preventing surgery due to treatment related toxicities that may make surgery not feasible. Neoadjuvant PD-1 pathway targeting therapies have not significantly precluded surgery in ongoing single agent studies. Furthermore, neoadjuvant everolimus was well tolerated prior to surgery in NSCLC and neoadjuvant sirolimus was well tolerated prior to surgery in head and neck squamous cell carcinoma patients. However, the risks of combination durvalumab and sirolimus are not known. The dose limiting toxicity assessment of combination therapy portion of this study must be completed as outlined in section 5.1. Furthermore, a low dose of sirolimus, which corresponds to the target immunologic dose, will be administered.

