3. STUDY DESIGN

3.1 Overview of study design

This is a Phase Ib open-label, single-arm study in newly diagnosed stage I-IIIA NSCLC patients, to test sirolimus in combination with durvalumab as neoadjuvant treatment prior to curative-intent surgical resection. The safety and tolerability as well as efficacy of combination sirolimus with durvalumab will be evaluated in this treatment setting. The study is also designed to investigate a number of laboratory correlative studies to define mechanisms of anti-tumor activity of sirolimus + durvalumab and several potential predictive biomarkers, which will help identify patients who are more likely to respond to treatment. Finally, the study will also include DFS and OS as secondary endpoints.

Up to 31 patients with NSCLC will be enrolled in this study at Emory University Winship Cancer Institute and affiliated sites. Enrollment will occur in 2 parts based on Simon 2 stage design, in which at least 2 of the first 16 patients must achieve pathologic complete response in order for the study to enroll 15 additional patients.

Eligible patients will complete 2 cycles of outpatient study treatment prior to proceeding to standard of care surgical resection. In order to allow a reliable assessment of the contribution of sirolimus versus durvalumab to the observed clinical and PD outcome, treatment will start with sirolimus 6mg orally for one loading dose followed by 2mg orally once daily three weeks prior to the start of durvalumab. Durvalumab will be administered at a dose of 1500mg Q 3 weeks starting on C1D1 for up to 2 cycles that are 21 days in length. Pharmacodynamic analysis will be done using PD samples collected at baseline (tissue) and with blood samples on day -7, C1D1 prior to durvalumab, C1D8, C2D1, C2D8 and at the time of surgery (blood and tissue). Additional post surgery blood samples will be collected at 1, 3, and 6 months post-surgery. See **study schedule of assessments** for schedule of Biomarker collection. Patients will proceed to surgery within a 4-week period post 2nd dose of durvalumab but not earlier than one week after the administration of durvalumab i.e. not earlier than C2D8. Additionally, patients will self-administer heavy water (D2O) 50ml orally three times a day from C1D1 through C1D5 followed by 50ml orally twice a day through the day prior to surgery in order to label dividing cells for research tracking purposes.

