4.4 Replacement of patients

Patients who withdraw consent prior to administration of durvalumab will be replaced. Patients who discontinue study treatment prematurely will not be replaced.

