11.2.2 Efficacy analyses

Primary Efficacy Endpoint

The effectiveness of sirolimus followed by durvalumab will be assessed by complete pathologic response rate in the efficacy population. If the null hypothesis is rejected then this is evidence that the response rate exceeds 10% when sirolimus followed by durvalumab is given before resection. The one-sided 95% confidence interval (CI) for complete pathologic response will be reported. Exact binomial test will be used to compare the estimated complete pathologic response rate to the historical reference.

Secondary Efficacy Endpoints

The complete pathologic response rates for PDL-1 negative and PDL-1 positive patients in the *efficacy population* will be presented separately.

A comparison of both the *complete pathologic response* and investigator assessed response rates per RECIST v1.1 rates between the PD-L1 positive and PD-L1 negative groups will be performed by calculating the lower bound of a one-sided 80% CI for the difference, complete pathologic response for PDL-1 positive patients – complete pathologic response for PDL-1 negative patients. Chi-square test or Fisher's exact test will be used to compare the efficacy in term of response rate between the different groups stratified by other factors, respectively. Logistics regression model will be further employed to test the adjusted effect of each other factor on the response rate after adjusting for other clinical factors and demographic factors, respectively. Correlation of response will be performed for tumor mutation burden using spearman correlation coefficient and tested with Wald's test.

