11.3 Determination of sample size

Pathologic complete response is rare following neoadjuvant chemotherapy but was reported in 0-8% of cases³⁹. The current study is designed to test improved rate of pathologic complete response from 10% to 25% treatment with sirolimus followed by durvalumab. Using a MinMax 2-stage design, a total of 31 patients will be enrolled in 2 stages. At the end of stage I, at least 2 of 16 patients must achieve complete pathologic complete response in order for the study to enroll 15 additional patients. The regimen of sirolimus followed by durvalumab will be considered to have sufficient efficacy to warrant further testing in this patient population if 6 or more of the 31 patients achieve a pathologic CR at the end of stage II. The study has 80% power at a 1-sided alpha of 0.1 to show a compelling 25% pCR compared to a less compelling rate of 10%. Because this is a signal finding study, an alpha of 0.1 is considered reasonable since any promising signal will be confirmed in a larger follow-up study.

Planned total number of patients is 31 over 2 years, with an estimated accrual rate of approximately 1-2 patients/month. Racial, ethnic, and gender accrual estimates below are based on 2010 Atlanta Census demographic information.

Accrual Targets			
Ethnic Category	Sex/Gender		
	Females	Males	Total
Hispanic or Latino	1	+ 1	= 2
Not Hispanic or Latino	14	+ 14	= 28
Ethnic Category: Total of all subjects	15 (A1)	+ 15 (B1)	= 30 (C1)
Racial Category			
American Indian or Alaskan Native	0	+ 0	= 0
Asian	1	+ 1	= 2
Black or African American	6	+ 6	= 12

Clinical Study Protocol

Investigational Drug Substance: MEDI4736 Sirolimus (Rapamune)

Study Number **19-20015**

Edition Number: 4

Date: **11 February 2022**

Native Hawaiian or other Pacific Islander	1	+	1	=	2
White	7	+	7	=	14
Racial Category: Total of all subjects	15	(A2)	15	(B2)	30 (C2)
(A1 = A2)		(B1 = B2)		(C1 = C2)	

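### The primary pCR rate, its bound and the exact test use resected, EGFR-non-mutant patients only, while continuation and success are judged on 2 of 16 and 6 of 31 enrolled patients, and nothing reconciles the two denominators

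*Combined protocol and SAP*

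**What the plan says.** **Analysis set.** Section 11.1.2 limits the primary and secondary efficacy analyses to "all enrolled patients who have received at least one dose of durvalumab, underwent resection and who do not have EGFR mutant tumors". The synopsis, under Efficacy Analyses, has the same restriction: "underwent resection and who do not have EGFR mutant tumors".

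**Primary analysis.** Section 11.2.2 states that effectiveness "will be assessed by complete pathologic response rate in the efficacy population". The one-sided 95% confidence interval and the exact binomial test against the historical reference follow in the same paragraph.

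**Decision rules.** Section 3.1 requires that "at least 2 of the first 16 patients must achieve pathologic complete response" before 15 more are enrolled. Section 11.3 gives 31 as the number to be enrolled and calls the regimen worth further testing "if 6 or more of the 31 patients achieve a pathologic CR at the end of stage II".

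**Replacement.** Section 4.4: "Patients who withdraw consent prior to administration of durvalumab will be replaced". It continues: "Patients who discontinue study treatment prematurely will not be replaced".

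**Failure to reach surgery.** Section 1.6.2: "Neo-adjuvant studies additionally pose the risk of delaying or preventing surgery due to treatment related toxicities". The same section reports that PD-1 pathway drugs given alone have not significantly precluded surgery, and that the risks of this combination are unknown.

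No section says that 16 or 31 means resected or evaluable patients, how an unresected patient is scored for pCR, or whether an EGFR-mutant patient counts toward 16 and 31. EGFR mutation is not among the exclusion criteria in section 4.2, so such patients can be enrolled.

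**The concern.** Resection happens after treatment starts, and the protocol itself says toxicity can prevent it. Conditioning the co-primary rate on resection therefore removes some treatment failures from the denominator. These patients are not replaced, so on a plain reading they remain among the 31 as non-responders for the count rule while leaving the rate, the bound and the test. The plan then has two statements about efficacy on different denominators: rejection of 10% by the exact test, and 6 or more pCRs out of 31. It does not say which governs if they differ.

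The EGFR condition is a second source of mismatch. It can remove a responder as well as a non-responder, so its effect can go either way.

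The same set also governs the secondary efficacy analyses. Section 9.1.2 defines RECIST evaluability without requiring resection, and section 8.1.3 follows all patients for survival. Restricting RECIST response and overall survival (OS) to resected patients would discard outcomes that are already being collected.

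**Working it through.** **Inputs.** Null 10%, alternative 25%, one-sided alpha 0.10, power 80%, 2 of 16 then 6 of 31 (section 11.3). One-sided 95% bound and exact test (section 11.2.2). That section gives no level for the test, so I use the design's 0.10. The documents give no unresected share *u*; 5, 10, 15 and 20% are assumed.

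**1. The plan's own figure.** P(success) = Σ (x = 2 to 16) Bin(x; 16, p) × P[Bin(15, p) ≥ 6 − x]. At p = 0.10 this is 0.0788; at p = 0.25 it is 0.8053. The stated alpha and power reproduce.

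**2. Reported rate, unresected patients the only exclusions.** With y pCRs and k excluded, the rate is y/(31 − k) instead of y/31, a factor of 1/(1 − u): 1/0.95 = 1.05, 1/0.90 = 1.11, 1/0.85 = 1.18, 1/0.80 = 1.25.

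**3. Exact test against count rule, same exclusions.** The test p-value with m analysed is P[Bin(m, 0.10) ≥ y]. The smallest y with p ≤ 0.10 is 6 for m = 26 to 31 and 5 for m = 19 to 25. So 5/26 gives p = 0.112, 5/25 gives p = 0.098 and 5/31 gives p = 0.193. A conflict needs at least 31 − 25 = 6 exclusions, and then the test passes while the rule fails.

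**4. How often.** Model: resected counts Bin(16, 1 − u) and Bin(15, 1 − u), no pCR without resection, and at least 2 pCRs in stage 1. An all-treated rate p corresponds to p/(1 − u) among resected patients.

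| Unresected | 5% | 10% | 15% | 20% |
|---|---|---|---|---|
| Test passes, rule fails: 10% among resected | 0.02% | 0.4% | 1.6% | 2.8% |
| same: 10% among all treated | 0.02% | 0.6% | 2.4% | 5.0% |
| same: 25% among all treated | 0.05% | 1.0% | 3.4% | 5.9% |
| same: 25% among resected | 0.06% | 1.2% | 4.7% | 9.4% |
| Type I error of the test, 10% an all-treated rate | 7.9% | 8.5% | 10.3% | 12.9% |
| Type I error of the test, 10% a resected-patient rate | 6.5% | 5.6% | 5.7% | 6.0% |

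**5. EGFR exclusion.** Suppose 6 of 31 enrolled have a pCR and one of the 6 is a resected EGFR-mutant patient, with no other exclusions. The rule is met at 6/31 = 19.4%. The efficacy set has 5/30 = 16.7%, p = 0.175, and the test fails. One patient is enough, and the reported rate falls.

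**6. Bound.** The one-sided 95% lower bound is the 5th percentile of Beta(y, m − y + 1). With 6 pCRs it is 8.8% at m = 31 and 10.15% at m = 27.

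**The case against.** **The go decision rests on a count of enrolled patients.** A reader might infer that leaving out unresected patients makes the success rule too easy to pass. The documents do not support that. Section 11.3 ties further testing to 6 of 31 enrolled, and an unresected patient cannot add to that count. This objection stands; the defect lies in the reported rate, bound and test.

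**The bound decides nothing.** It is tempting to read the move from 8.8% to 10.15% as a false success. Section 11.2.2 only reports the 95% bound, and its level does not match the design alpha of 0.10. At the matching one-sided 90% level, the bound for 6/31 is already 10.5% with nobody excluded. The shift is descriptive only.

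**Stopping sirolimus does not by itself remove a patient.** Section 4.3 keeps patients who discontinue treatment in the study. They leave the efficacy set only if durvalumab or resection is also missed, or if the tumour is EGFR mutant.

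**Losses may be small.** Single-agent experience cited in section 1.6.2 is reassuring, and at 5 to 10% unresected the test and the rule conflict in 1.2% of trials or fewer in the scenarios above. That is fair, but the same section calls the combination's risks unknown, and the reported rate shifts from the first exclusion.

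**Resected-only pCR is a defensible quantity.** Section 2.1 measures pCR at resection, and section 11.2 summarises discontinuations, so an all-treated rate could largely be reconstructed. This supports keeping the resected-only rate as a supportive result. It does not settle which denominator is primary.

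**Conclusion.** The concern holds in limited form and should be fixed. The co-primary rate, its bound and the exact test use a different denominator from the decision rules, and the plan neither reconciles them nor says how unresected and EGFR-mutant patients count.

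If unresected patients are the only exclusions, the reported rate is overstated relative to all treated patients by 5 to 25% in relative terms over the assumed range. Conflict with the count rule is then rare at low loss and runs one way. Type I error of the resected-only test exceeds 0.10 only from about 15% unresected, and only if the 10% reference is an all-treated rate; the documents do not say which it is. With EGFR exclusions neither the direction nor the six-patient threshold holds.

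The frequencies assume the listed unresected shares, no EGFR exclusions, and non-resection unrelated to what the response would have been.

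**What to change.** In sections 11.1.2, 11.2.2 and 11.3 and the synopsis:

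- Define one primary pCR set: all patients who started study treatment, except consent withdrawals before durvalumab, who are replaced under section 4.4. List those withdrawals with reasons.
- Score every patient without a resection as non-pCR.
- Use this set for the rate, the bound, the exact test and the 2/16 and 6/31 rules.
- State whether EGFR-mutant patients count toward 16 and 31, determined from pre-treatment tissue, and apply the same choice to the rate and the rules.
- State that the 10%, the 25% and the 80% power refer to this set.
- Keep resected-only pCR as a supportive analysis.
- Use the section 9.1.2 evaluable set for RECIST response and all treated patients for OS.

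**Cost.** Wording only; no extra data. The reported pCR rate will usually be lower. If 25% is an all-treated rate, power of the 6/31 rule stays at 80.5%. If 25% is a resected-patient rate, putting p = 0.25(1 − u) in the step 1 formula gives 76.0%, 70.9%, 65.0% and 58.7% at 5, 10, 15 and 20% unresected. That loss is already present in the 6/31 rule as written. Against the resected-only exact test (76.1%, 72.1%, 69.8%, 68.0%), it is 0.1, 1.2, 4.7 and 9.4 points lower.
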